Some studies have already been conducted in order to investigate the effects of different cleaning protocols for acrylic removable orthodontic appliances and may also help to reduce the risk of oral diseases related to biofilm growth, some different processes have been described such as denture cleaners, enzymatic solutions, chlorhexidine, sodium hypochlorite, or homemade solutions containing vinegar or citric acid (**Eichenauer *et al.*, 2011**). The two major approaches used for denture cleaning are mechanical and chemical methods. Mechanical methods include brushing (using water, soap, toothpaste, or abrasives) and ultrasonic treatment. Mechanical cleaning with brushes is inexpensive and common, but elderly and disabled patients might face difficulties with this method because of poor motor coordination, poor dexterity, and low motivation. There is evidence that mechanical cleaning with toothpastes can result in significant wear of conventional acrylic resins. Chemical method includes immersion of dentures in different cleansing solutions. Immersion in cleansing solution is an inexpensive, easy, and comfortable alternative procedure. Moreover, the cleansing solution can reach undercuts of the denture base that are difficult to clean mechanically, resulting in more efficient cleaning (**Schwindling *et al.*, 2014**).

No study is conducted to evaluate the most effective method used to remove biofilm from removable orthodontic appliance.

Research question:

What is the most effective method of cleaning an acrylic based removable orthodontic appliance?

Research hypothesis

The null hypothesis: There is no difference between the different methods of cleaning acrylic based removable orthodontic appliances.

Aims of the study:

The aims of the current study are:

1. To evaluate the effects of different cleaning regimes i.e. chemical and mechanical on biofilm formation of an acrylic based removable orthodontic appliance.
2. To find out if surface modification i.e. polished acrylic fitting surface, have an impact on cleaning the biofilm formation.

Methodology

Study design:

An in vivo study.

Setting:

It is double-blind, parallel, randomized clinical trial conducted in the orthodontic clinic after obtaining the ethical approval from the ethics committee of the department.

Subjects:

Orthodontic patient will be selected to wear a removable appliance for the study period.

Sample size:

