Thirteen orthodontic patients for each group will be selected to wear a removable orthodontic appliance for the study period (**Lima et al., 2006**) and will be instructed for the cleaning protocol according to the manufacturer's instructions.

Inclusion criteria:

- Presence of full upper permanent dentition;
- Well-aligned teeth or mild crowding (less than 3mm);

- No history of sensitivity to any ingredient contained in the cleaning materials;
- Nonsmoker;
- Caries free.

Exclusion criteria:

- Participant taking steroid-based or antibacterial mouthwash or broad-spectrum antibiotics;
- Mouth breather;
- Participant taking medication that reduces salivary flow;
- Pregnant or lactating female (**Albanna *et al.*, 2017**).

All of the study steps were explained to the participants verbally and in writing, written informed consent will be obtained from each participant.

Materials and instruments**Materials used for orthodontic removable appliance fabrication:**

- Acrylic powder and monomer (Orthocryl, Dentaaurum, Ispringen, Germany).
- 0.7 mm stainless steel wire (Spring hard, Dentarum, Ispringrn, Germany).
- Adam's plier.
- Sticky wax.
- Separating medium.
- Cutter.
- Wax knife.
- Mold material.

Materials used for cleaning regimes:

- 1-Brush (dental or denture brush) with chlorhexidine (CHX) toothpaste.
- 2-Chemical cleaning i.e. Lacalut cleaning tablet.
- 3-Combination of brushing with CHX toothpaste and cleaning tablet.

Materials and equipment used form microbial isolation and identification:

1. Calcium alginate swab.
2. Calgon ringer solution.
3. Bijou tube.
4. Glass beads.
5. Phosphate buffered saline (PBS).
6. Anaerobic cabinet.
7. Vortex machine.
8. Culture media.

A. Mitis-Salivarius Agar (MSA): This agar is a commonly used selective medium for isolating and quantifying *S. mutans* in many cariology clinical and epidemiological studies (**Xiao *et al.*, 2016**).

B. Mannitol salt agar: Is a commonly used selective and differential growth medium in microbiology. It contains a high concentration (about 7.5%-10%) of salt (NaCl), making it selective for Gram-positive *Staphylococcus aureus* and *epidermidis* since this level of salt is inhibitory to most other bacteria (**Bachoon *et al.*, 2008**).

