C. Blood agar: is enriched medium used to culture those bacteria or microbes that do not grow easily. Such bacteria are called “fastidious” as they demand a special enriched nutritional environment as compared to the routine bacteria (**Sirois, 2020**).

Other materials:

- 1- Rubber bowl
- 2- Type IV stone
- 3- Gloves
- 4- Masks

5- Plastic petri dish

Procedure

Construction of acrylic samples with different surface texture:

Acrylic samples i.e. tiles of different surface texture will be made. An acrylic sheet of 1 mm thickness will be made using a mold with technique as shown in figure 3.

[figure not shown]

Figure 1: Acrylic samples made from polished and unpolished acrylic sheet.

A half of the sheet will be polished using a conventional polishing technique until a glossy surface appears, whereas, the remaining will be kept without modification. Tiles of 5mm in diameter will be bored using a trephine bur on both sides of the acrylic sheets and each set of tiles i.e. the polished and unpolished samples, will be color coated from its seated surface.

Construction of upper removable orthodontic appliance

An impression will be taken to the maxillary arch using alginate impression material (Hydrogum 5, Zhermack, Badia Polesine, Italy). The negative replica is then poured using type IV stone to make a study model. Four metal discs (5mm in diameter and 1.2mm thickness) will be placed on both sides of the palate as seen in figure 2; A.

[figure not shown]

Figure 2: Construction of the acrylic based orthodontic appliance. A, Study model with acrylic tiles; B, Fitting surface of the acrylic removable appliance.

The wire framework of the removable appliance will be fabricated using a 0.7 mm in diameter stainless steel wire (Spring hard, Dentarum, Ispringen, Germany) to make Adam's clasps on upper first premolars and molars to retain the appliance.

After applying a separating medium, an acrylic base will be fabricated using the orthodontic acrylic powder and liquid (Orthocryle, Dentaurum, Ispringen, German) with a ratio of (2.5 parts powder to 1 part liquid) according to the manufacturer's instruction. Before setting, a sprue or chimney like structure will be created through the acrylic dough to facilitate the metal discs and acrylic sample removal. The appliance then will be removed and the metal tiles will be dislodged using metal pin (Figure 2; B).

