The acrylic tiles (5mm in diameter and 1mm thickness) will be placed and fixed into the holes, created by the metal discs, using sticky wax. The acrylic samples will be randomly seated as shown in figure 3.

The appliance will be sterilized using proper sterilization protocol.

Figure 3: The acrylic base containing the acrylic samples.

Method for biofilm detection

The removable appliance will be assigned randomly and blindly and fitted into the oral cavity of the patient for one week. Each individual will be given a pack containing the cleansing pack and an instruction sheet with a web link describing the cleaning regimen for his/ her appliance. The packs are similar in shape and color and will be prepared by a third person who does not know the purpose of the study. The volunteer will be grouped into three groups:

Group 1: patients will be instructed to brush both sides of the removable appliance once a day for 1 minute before bedtime using the toothbrush and the CHX toothpaste provided and water (**Albanna *et al.*, 2017**).

Group 2: patients will be instructed to immerse the appliance in 150 ml cup with tap water and dissolve one cleansing (**Albanna *et al.*, 2017**) tablet for 20 minutes according to the manufacture instructions.

Group 3: Combination of the chemical and mechanical methods first submitted to the mechanical method, followed by the chemical method (**Oliveira *et al.*, 2009**).

At the end of the study period, the acrylic samples will be removed carefully and applied into a petri dish containing PBS via a sterile tweezer. The samples will be then immersed twice in a 25ml sterile tubes containing

PBS to remove the planktonic bacteria and inserted into 5ml bijou tube containing 1mm PBS and 5 sterile glass beads. The sample will be vortex-mixed for 1 min to disseminate the biofilm and create a homogenous solution. Ten-fold serial dilutions will be carried out in PBS before the samples are plated onto blood agar (BA), to give the total anaerobic count, mitis salivarius agar (MS), a selective agar for streptococci and Mannitol salt agar (MA) for Staphylococci spp. BA and MS plates will be incubated anaerobically for 2-4 days at 37°C using anaerobic cabinet whereas the MA will be incubated for 2 days in aerobic condition. All organisms from both selective and nonselective agars will be distinguished by colony morphology and will be characterized by Gram reaction (**Al Groosh *et al.*, 2011**) and other confirmatory tests.

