Confirmatory test

1. Catalase testing: Catalase is a common enzyme found in nearly all living organisms exposed to oxygen (such as bacteria, plants, and animals) (**Chelikani *et al.*, 2004**). This test demonstrates the presence of catalase, an enzyme that catalysis the release of oxygen from hydrogen peroxide (H₂O₂). The catalase test is mainly used to differentiate between Gram-positive cocci: members of the genus Staphylococcus are catalase-positive, and members of the genera Streptococcus and Enterococcus are catalase-negative (**Whittenbury, 1964**).
2. Coagulase testing: Coagulase is a protein enzyme produced by several microorganisms that enables the conversion of fibrinogen to fibrin. In the research laboratory, it is used to differentiate between different types of Staphylococcus isolates. Importantly, *S. aureus* is generally coagulase-positive (**Ryan and Ray, 2004**).

Statistical analysis

All the data of the tested samples will be collected and analyzed using SPSS (statistical package of social sciences). In this study the following statistics will be used:

Descriptive statistics

- Mean.
- Standard deviation (SD).
- Minimum and maximum values.
- Statistical tables, figures and charts.

Normality test

Data distribution will be tested first using Shapiro-Wilk test to find that whether our collecting data are normally distributed or not.

Inferential statistics

- ANOVA (if the data parametric) or Kruskal Wallis test (if none parametric) to compare the effect of each cleaning agents on biofilm reduction of removable orthodontic appliance and Tukey HSD pot hoc test if there is significant difference between them.
- Independent t-test (if the data parametric) or Mann Whitney test (if none parametric) to compare the effect of each cleaning agents on biofilm reduction on polished and unpolished surface

In the statistical evaluation, the following levels of significance will be used:

Non-significant NS $P > 0.05$

Significant S $0.05 \geq P > 0.01$

Highly significant HS $P \leq 0.01$

Time table:

Duty	Expected time
Patient Identification and allocation	4 months
Intervention period	3 months
Data collection and analysis	2 months
Writing up the thesis	10 months (starting from the beginning of the study)
Total expected time to finish	About 10 to 11 months

Budget and Funding: The study is self-funded

Dissemination: Master Thesis.

References

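### Aim 2 is tested with an unpaired test although polished and unpolished tiles appear to share a mouth, so the surface comparison loses power the data could give.

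*Combined protocol and SAP*

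**What the plan says.** The second item under Aims of the study is "To find out if surface modification i.e. polished acrylic fitting surface, have an impact on cleaning the biofilm formation".

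The Inferential statistics list has two entries. The first compares the cleaning regimens by ANOVA or Kruskal-Wallis, followed by Tukey HSD. The second is an independent t-test, or a Mann-Whitney test if the data are not normal, "to compare the effect of each cleaning agents on biofilm reduction on polished and unpolished surface". No paired test, repeated-measures or mixed model, or interaction term is listed.

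On design, the sample size section states that "Thirteen orthodontic patients for each group will be selected to wear a removable orthodontic appliance for the study period". Under Method for biofilm detection, "The volunteer will be grouped into three groups", which gives 3 x 13 = 39 patients. For the appliance, "Four metal discs (5mm in diameter and 1.2mm thickness) will be placed on both sides of the palate"; these discs form the holes for the acrylic tiles. Of the tiles, "each set of tiles i.e. the polished and unpolished samples, will be color coated from its seated surface", and "The acrylic samples will be randomly seated as shown in figure 3". That figure is not available here, and the text does not say how many tiles of each finish go into one appliance.

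**The concern.** Random seating within the appliance and colour coding on the hidden side make most sense if each appliance carries both finishes. Surface is then a within-patient factor. An independent-samples test treats the polished and unpolished counts as if they came from different people, so variation between patients in overall bacterial load stays in its standard error. That variation cancels in each patient's polished-minus-unpolished difference.

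What is at stake is Aim 2: a real effect of polishing could be missed that the same 39 patients could show. The wording also leaves open whether there is one test per regimen (13 patients each) or a single pooled test. Neither reading gives a surface estimate that uses all 39 patients and also allows for regimen and for the shared mouth.

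**Working it through.** **Inputs from the plan.** Three groups of 13, so 39 patients; four tile sites per appliance; two finishes; significance at P of 0.05 or less.

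**Assumptions, because the plan gives no effect size, SD or correlation.** One mean per surface per patient; normal data with SD 1 on the analysed scale; both surfaces in every mouth; two-sided testing; a surface effect of 0.5 SD, equal in every regimen and held fixed as the correlation r varies over 0, 0.3, 0.5 and 0.7. The plan has no power figure for this comparison to reproduce.

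**Step 1: standard errors over 39 patients.** The unpaired test uses about sqrt(2/39) = 0.226 whatever r is. The true standard error of the polished-minus-unpolished mean is sqrt(2(1 - r)/39), which is 0.226 / 0.190 / 0.160 / 0.124 at r = 0 / 0.3 / 0.5 / 0.7.

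**Step 2: within-patient analysis.** The SD of the difference is sqrt(2(1 - r)). The noncentrality is 0.5 x sqrt(39) / sqrt(2(1 - r)), with 36 df after allowing for regimen. At r = 0.5 this is 0.5 x 6.245 / 1 = 3.12, which gives 86% power.

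**Step 3: the planned test, simulated on the same data.**

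| Correlation r | 0 | 0.3 | 0.5 | 0.7 |
|---|---|---|---|---|
| Unpaired, per regimen (13 v 13) | 23% | 20% | 16% | 12% |
| Paired, per regimen (n = 13) | 22% | 29% | 38% | 57% |
| Unpaired, pooled (39 v 39) | 59% | 60% | 62% | 65% |
| Within-patient, all 39 | 58% | 73% | 86% | 98% |

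The third and fourth rows isolate the cost of ignoring the pairing. The first and fourth rows mix two changes: at r = 0.5, pairing alone moves 16% to 38%, and going from 13 to 39 patients moves 38% to 86%.

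**Step 4: type I error of the unpaired test.** Against a nominal 5%, it is about 2% / 0.9% / 0.2% per regimen at r = 0.3 / 0.5 / 0.7, and about 2% / 0.6% / 0.1% pooled. The test errs towards caution.

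**Step 5: regimen x surface.** This is a one-way F test on the within-patient differences, with 2 and 36 df. If one regimen differs by 0.8 SD of the difference, the noncentrality is 13 x 0.8² x 2/3 = 5.55 and power is about 51%.

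**Step 6: separate verdicts.** If the surface effect is truly equal in all regimens and each per-regimen test has power p, the three verdicts differ with probability 1 - p³ - (1 - p)³. With p = 0.163 (r = 0.5, unrounded) this is 1 - 0.004 - 0.586 = 0.41. A mixture of S and NS labels is therefore weak evidence that regimens differ.

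**The case against.** The strongest reply has four parts.

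- **Same-mouth placement is inferred.** This stands. The layout is in a figure that is not available here, and the power loss is conditional on it.
- **A pooled test is not biased.** If every patient contributes equally to both surfaces, the pooled mean difference equals the within-patient estimate; only the standard error differs. This stands too, and at zero correlation nothing is lost.
- **No aim asks for an interaction test.** A reader might infer that the plan fails to deliver a promised regimen x surface analysis, or that it will compare S and NS labels between regimens. The documents support neither. Aim 2 can be read as a single surface effect, the stated null hypothesis concerns cleaning methods, and no comparison of labels is planned. The interaction is therefore a useful secondary estimate, and at 3 x 13 a weak one.
- **The contrast of 16% with 86% overstates the role of pairing.** Correct: much of it is 13 patients against 39. Disagreement between per-regimen verdicts also reflects small groups. Three paired tests at 38% power would disagree more often, in about 1 - 0.38³ - 0.62³ = 71% of trials.

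What remains is that the listed test does not fit the apparent design, and a better one needs no further data.

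**Conclusion.** The concern holds as an avoidable loss of efficiency on the second aim. If both finishes share a mouth and same-mouth counts are positively correlated, pooled power for a 0.5 SD surface effect is about 60% to 65% where a within-patient analysis would have 73% to 98% (correlation 0.3 to 0.7). If the tests are run per regimen, power is about 12% to 20%, partly because each uses only 13 patients.

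A reader might go further and infer that the planned test would produce false positive surface effects. The documents do not support that. With one mean per surface per patient and positive correlation, the test is conservative. If two tiles per surface were entered singly (assumed; the plan does not say), its type I error could lie on either side of 5%, at about 1% to 9% depending on how variance divides between patient, surface within patient, and tile. No direction is claimed for that case.

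The effect size and correlations are assumptions. The regimen comparison in the first bullet is not affected by this point.

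**What to change.** State how many polished and unpolished tiles each appliance carries. Then, for each culture count, replace the second bullet with one mixed-design ANOVA or mixed model in SPSS on patient-by-surface means: regimen between patients, surface within patients, and regimen x surface.

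- Use the overall surface effect, with its 95% CI, to answer Aim 2.
- If the data are not normal, apply a Wilcoxon signed-rank test to each patient's polished-minus-unpolished difference over all patients.
- Report regimen x surface as a secondary estimate with 95% CIs. Do not read a non-significant result as equal effects, and do not infer regimen differences from separate S and NS labels.
- If an interaction is clearly present, give the surface effect by regimen with CIs alongside the overall effect.
- If each appliance in fact carries only one finish, use a two-way ANOVA (regimen, surface, regimen x surface) on patient means.

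The cost is a change of wording in the statistics section, with the same patients, data and software. The downside is that per-regimen surface tests become secondary, and the interaction estimate will be imprecise.

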Orthodontic treatment is adopted by wide section of society not only for the corrections of malocclusion but also improves mastication, speech and appearance, as well as overall health, comfort, and self-esteem (**Westley, 2010**). There are two types of orthodontic appliances either removable or fixed appliance. Although the orthodontic appliance has many known benefits, these appliances are also associated with a number of damages and disorders of oral cavity (**Pathak and Sharma, 2013**). Polymethyl methacrylate (PMMA) is the standard material for denture bases because of its biocompatibility, low cost, ease of processing, high flexural resistance and flexural modulus, and low water solubility (**Leão *et al.*, 2018**); however, the PMMA denture base is susceptible to microbial colonization in the oral environment (**Puri *et al.*, 2008**) other factors that favor microbial colonization are porosity, surface roughness, poor denture hygiene, and continual and nighttime wearing of dentures (**Gendreau and Loewy, 2011**). Rougher surfaces have been found to be more difficult to clean and promote re-growth by surviving organisms as opposed to complete surface re-colonization (**Teughels *et al.*, 2006**).

Physiologically the human's oral microflora consists of a mixture of organisms, which are common also to other anatomical districts. This bacterial charge is extremely complex, being composed of over 700 different

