The denture base after processing is finished using acrylic finishing bur and sandpaper and polished using a rag wheel and cone with pumice slurry. The surface roughness of the denture base material has a substantial effect on plaque adherence and microbial colonization of the prostheses. A rough surface creates niches in which microorganisms are protected against mechanical dislodging forces. The bacteria can subsequently spread over the denture surface from these niches. It has been proven that an increase in surface roughness above a threshold of 0.2 μm results in a simultaneous increase in plaque accumulation. This concept is of clinical importance because patients need to have a smooth surface to deter the formation of a biofilm. This is an esthetic concern as well as an overall concern for maintaining good oral hygiene. **Bollen et al. (2017)** found that the surface roughness of acrylic resin can be dependent on the polishing grit. *Streptococcus sanguis*, *Bacteriodes gingivalis*, and *Candida albicans* adhere in very high numbers to roughened acrylic resin versus smooth acrylic resin. **Al Groosh et al. (2015)** investigated the influence of surface roughness and surface dynamics on the attachment of Methicillin-Resistant *Staphylococcus aureus* (MRSA) onto orthodontic retainer materials and found that the number of bacteria attached to the surface of the tested materials increased over the 48 h time period regardless of the material chemistry and surface topography. There was no significant difference in MRSA biofilm formed on the surface of these materials. However, the scanning electron microscope and the Confocal laser scanning microscopy showed that the distribution of bacterial aggregates increased on the rougher surface of the auto polymerized acrylic samples whereas the pattern of bacterial attachment was more uniformly distributed on the thermoplastic samples.

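### The polished-versus-unpolished test is labelled biofilm reduction, but only residual counts exist, so it cannot show that polishing improves biofilm removal

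*Combined protocol and SAP*

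**What the plan says.** All references are to the combined protocol and SAP.

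- **Aim 2** (Aims of the study): "To find out if surface modification i.e. polished acrylic fitting surface, have an impact on cleaning the biofilm formation".
- **Planned test** (Statistical analysis, Inferential statistics): an independent t-test, or Mann-Whitney if not normal, "to compare the effect of each cleaning agents on biofilm reduction on polished and unpolished surface". The ANOVA / Kruskal-Wallis line for the three regimens also calls its outcome a reduction.
- **Starting state** (Construction of upper removable orthodontic appliance): "The appliance will be sterilized using proper sterilization protocol".
- **Measurement** (Method for biofilm detection): one week of wear under brushing, tablet, or both. Tiles are then removed and plated on three media. All three counts come from that one time point. No pre-cleaning count, uncleaned tile or uncleaned group is described.
- **Layout**: "Four metal discs (5mm in diameter and 1.2mm thickness) will be placed on both sides of the palate". Polished and unpolished tiles form two colour-coded sets, and "The acrylic samples will be randomly seated as shown in figure 3". That figure is not available to this review.
- **Premises** (introduction): roughness above a threshold "results in a simultaneous increase in plaque accumulation". Separately, "Rougher surfaces have been found to be more difficult to clean and promote re-growth by surviving organisms".

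**The concern.** A reduction needs something to be reduced from. The tiles start sterile and are cultured once, so each count is what was deposited (and regrew) minus what cleaning removed.

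The introduction gives two routes to a higher count on unpolished tiles: they collect more, or they are harder to clean. Only the second is an effect on cleaning. The planned test sees the sum of the two and cannot divide it.

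A significant result could therefore be reported as polishing improves cleaning when polished tiles had simply collected less. If the test is run once per regimen, as the wording suggests, significance in one group and not in another could be reported as a regimen-specific benefit without any direct comparison.

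A second, conditional issue is that the test treats the two surfaces as independent samples, although the layout implies that each patient contributes both.

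**Working it through.** The plan gives no effect size, SD, correlation or power for this comparison. The 13 per group rests on a citation, so there is no planned figure to reproduce. Every numerical input below except 13 per group, 39 in total (3 × 13) and the 0.05 level (taken as two-sided) is an assumption.

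**1. Attribution**

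On the log scale, expected gap (unpolished − polished) = accumulation gap + removal deficit on unpolished tiles. A 1.0 log10 gap arises equally from (1, 0), (0, 1), (0.5, 0.5) or (2, −1). One end-of-week count gives one equation in two unknowns, and a larger sample does not help.

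As an illustration, let A be the deposit between cleanings and r the share removed at each cleaning:

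B_t = (B_{t−1} + A)(1 − r), B_0 = 0, t = 1 to 7.

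B_7 is proportional to A. Doubling A on unpolished tiles with the same r gives log10(2) = 0.301 for any r. This still holds if one further deposit follows the last cleaning, since B_7 + A is also proportional to A.

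Conversely, equal deposits give the same 0.301 gap with these removal shares:

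| Polished r | Unpolished r, sampled right after a cleaning | Unpolished r, one further deposit before sampling |
|---|---|---|
| 50% | 32.0% | 21.5% |
| 90% | 81.8% | 44.6% |
| 99% | 98.0% | 49.3% |

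The matching shares depend heavily on when tiles are sampled, which the plan does not fix relative to the last cleaning. They also assume daily cleaning, which is documented only for Group 1. That the two routes cannot be separated does not depend on either.

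**2. How often accumulation alone gives significance**

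Inputs: identical cleaning on both surfaces, SD 1 log10, 13 values per surface, within-patient correlation 0 or 0.5, 20,000 simulated trials. The planned independent t-test is significant in:

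- 16% to 23% of trials for an accumulation gap of 0.5 log10;
- 69% to 74% for 1.0;
- 96% to 99% for 1.5.

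These are correct detections of a residual difference. They would be wrong as evidence about removal.

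**3. Pairing, if both surfaces are on each appliance**

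The independent test uses SE = SD × √(2/n). With within-patient correlation ρ, the true SE is SD × √(2(1 − ρ)/n). The ratio √(1 − ρ) is 0.84, 0.71 and 0.55 at ρ = 0.3, 0.5 and 0.7, so the planned SE is too large.

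Simulation (20,000 trials per cell, SD 0.8 to 1.0, ρ 0.3 to 0.7):

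| | Independent | Paired |
|---|---|---|
| Rejection at zero gap, one regimen (13) | about 0.1% to 2.4% | about 5% |
| Power at 0.3 to 0.5 log10, one regimen (13) | about 3% to 31% | about 13% to 76% |
| Power at 0.3 to 0.5 log10, all 39 | about 13% to 91% | about 34% to over 99% |

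95% CI half-width for the overall gap:

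- independent, t(76) × SD × √(2/39): 0.36 to 0.45;
- paired, t(38) × SD × √(2(1 − ρ)/39): 0.20 to 0.38.

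**4. Comparing polish gaps between regimens**

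With 13 within-patient differences per group and one group shifted by 0.5 log10, the F(2, 36) test has power of 17% to 52% over the same SD and ρ ranges.

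**The case against.** **Aim 2 may ask only about net residue.** Its wording is loose, and Aim 1 speaks of effects on biofilm formation, itself a net outcome. The stated null hypothesis concerns cleaning methods, not surface. Read that way, the comparison answers the aim and only the word reduction is wrong. This stands, and it is why the point is about labelling and interpretation, not an invalid test.

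**The accumulation route is not certain.** The introduction cites a study of retainer materials in which "There was no significant difference in MRSA biofilm formed on the surface of these materials". That leaves the size of any accumulation gap open. It does not let the trial assume that the gap is zero.

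**Pairing is a separate issue.** It is: a paired analysis does not solve attribution. It also depends on a layout that four sites, two colour-coded tile sets and random seating imply but that the available text does not state outright.

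**Stronger readings that the documents do not support.**

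- A reader might infer that the trial cannot compare cleaning methods. It can: the groups are randomized, and residual counts can be compared between them.
- A reader might infer that the independent test inflates false positives. With positive within-patient correlation it does the opposite.
- A reader might infer that a very small removal difference mimics a doubled deposit. That holds only if tiles are sampled straight after a cleaning; with one further deposit, 90% is matched by 44.6%, not 81.8%.

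**Conclusion.** The concern holds in a limited form. The plan names an outcome that the trial does not measure. A polished-unpolished difference will be evidence about residual biofilm under cleaning, not about removal. This follows from the design (sterile start, cleaning in every group, one time point) and needs no assumed number. The 0.30 log10 example shows only that a plain twofold difference in deposit reproduces the gap with identical cleaning.

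The loss from ignoring pairing is conditional on both surfaces sharing an appliance and on the assumed SD of 0.8 to 1.0 log10 and correlation of 0.3 to 0.7. Under those assumptions it is material: with 39 patients, power is about 13% to 91% independent against 34% to over 99% paired.

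The change should be made because it alters what the second aim can conclude, on the same patients, tiles and plates. Aim 1 is unaffected apart from the outcome's name.

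**What to change.** 1. In both inferential lines, replace biofilm reduction with residual log10 CFU per tile at one week, for each of the three counts. The log scale needs a rule for zero counts fixed in advance.
2. Restate Aim 2 as the effect of polishing on residual biofilm under cleaning. Add that, without an uncleaned reference or a pre-cleaning count, no claim that polishing improves biofilm removal will be made.
3. State whether each appliance carries both surfaces. If so, average the tiles of each surface within a patient. Analyse the unpolished-minus-polished difference over all 39 patients by paired t-test, or Wilcoxon signed-rank if not normal, with a 95% CI.
4. Make any claim of a regimen-specific polish effect only from a direct comparison of these differences across the three groups (one-way ANOVA or Kruskal-Wallis). Label it low-power and about residual counts. Do not base it on separate per-regimen p-values, and do not read a non-significant result as equal effects.

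**Cost:** wording and SAP changes only, with no extra patients, visits or cultures. The downside is narrower claims, slightly more analysis, and an explicit statement that the removal reading of Aim 2 cannot be answered by this design.
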